2.2.2 Exclusion Criteria

A subject is excluded for any of the following reasons:

1. Prism in the refractive correction at time of enrollment (eligible only if prism is discontinued 2 weeks prior to enrollment).
2. Myopia greater than -6.00D spherical equivalent in either eye.
3. Previous intraocular or refractive surgery.
4. Known skin reactions to patch or bandage adhesives
5. Any treatment for amblyopia (patching, atropine, Bangerter filter, or vision therapy) during the past 2 weeks. Previous amblyopia therapy is allowed regardless of type, but must be discontinued at least 2 weeks immediately prior to enrollment.
6. Ocular co-morbidity that may reduce visual acuity determined by an ocular examination performed within the past 7 months (*Note: nystagmus per se does not exclude the subject if the above visual acuity criteria are met*).
7. No Down syndrome or cerebral palsy
8. No severe developmental delay that would interfere with treatment or evaluation (in the opinion of the investigator). Subjects with mild speech delay or reading and/or learning disabilities are not excluded.
9. Heterotropia or heterophoria with a total ocular deviation $>10\Delta$ (phoria plus tropia $>10\Delta$) at near (measured by PACT).

2.3 Historical Information

Historical information to be elicited will include the following: date of birth, sex, race, ethnicity, and history of prior eye-related treatment (including length of spectacle wear).

2.4 Procedures at the Enrollment Visit

All examination procedures must be tested within 7 days prior to the date of enrollment, except the cycloplegic refraction and ocular examination, which may be performed within 7 months prior to enrollment. All examination procedures at enrollment are performed in the subject's current correction, if required (testing in trial frames is not permitted), and without cycloplegia:

1. Distance Visual Acuity Testing: Monocular distance visual acuity testing will be performed in current refractive correction (if required) in each eye by a certified examiner using the electronic ATS-HOTV visual acuity protocol for children <7 years and the E-ETDRS visual acuity protocol for children ≥ 7 years on a study-certified acuity tester displaying single surrounded optotypes as described in the *ATS Testing Procedures Manual*.
 - Testing must be completed without cycloplegia and with spectacles or contact lenses, if worn (trial frames not allowed at enrollment)
 - The same visual acuity protocol will be used throughout the study regardless of age at follow-up.
2. Stereoacuity Testing:
 - Stereoacuity will be tested at near in current refractive correction using the Randot Butterfly and Randot Preschool stereoacuity tests.
3. Ocular Alignment Testing:
 - Ocular alignment will be assessed in current refractive correction by the cover/uncover test, simultaneous prism and cover test (SPCT), and prism and alternate cover test (PACT) in primary gaze at distance (3 meters) and at near (1/3 meter) as outlined in the *ATS Procedures Manual*.
 - See *section 2.2.1* for eligibility criteria related to ocular alignment.
4. Additional Clinical Testing:
 - Ocular examination as per investigator's clinical routine (if not performed within 7 months)
5. Nonius Cross Alignment
 - Subjects will be tested to see if they are able to align the nonius cross presented on the iPad. Subjects unable to fuse the cross are not eligible for the study.
6. Demonstration of Game Understanding
 - Subjects must demonstrate that they understand the game by scoring at least one completed line while playing the game set to the easy level in the office. Subjects unable to score a line are not eligible for the study.

2.5 Randomization of Eligible Subjects

The Jaeb Center will construct a Master Randomization List using a permuted block design stratified by site and age subgroup (5 to <7 years versus 7 to <13 years) in the younger cohort (5 to <13 years), and stratified by site and baseline amblyopic-eye visual acuity (20/40 to 20/80 (53 to 72 letters) and 20/100 to 20/200 (33 to 52 letters)) in the older cohort (13 to <17 years), which will specify the order of treatment group assignments. Although we would ideally stratify by each of three factors (site, age subgroup, and baseline amblyopic acuity) in both the younger and older cohorts, this was unlikely to achieve the desired balance given the proposed sample size, and so the

2 most important factors were chosen, within each age cohort, for stratification. Randomization will not be stratified by presence of a tropia since diagnosis of a microtropia is problematic.

All eligible subjects enrolled in the study will be randomly assigned in a 1:1 allocation to one of the following groups for each of the age cohorts:

1. Binocular treatment group: binocular computer game play 1 hour per day, 7 days per week (minimum of 4 days per week)
2. Patching group: Patching 2 hours per day, 7 days per week.

Once a child is assigned to treatment, he/she will be included in the analysis regardless of whether or not the assigned treatment is received. Thus, the investigator must not randomly assign a subject to treatment unless convinced that the parent will accept either of the treatments.

CHAPTER 3: TREATMENT AND FOLLOW-UP

3.1 Binocular Computer Game Treatment

All subjects in the study will play the Hess Falling Blocks game presented on an iPad while wearing red/green (anaglyph) glasses (over current spectacles, if applicable) with the green filter placed over the amblyopic eye. The subject should be instructed to hold the iPad at his/her usual reading distance. Some boxes are only visible to the fellow eye viewing through the red lens, while other boxes are only visible to the amblyopic eye viewing through the green lens. Image contrast varies depending on depth of amblyopia to ensure stimulation of the amblyopic eye and binocular game play.

Contrast of the falling shapes in the amblyopic eye will be at 100% throughout the study. Contrast of shapes seen by the fellow eye will begin at 20% at the start of the study and will increase or decrease automatically in 10% increments from the last contrast level (e.g., 20% to 22%) in a 24-hour period based on the subject's performance and duration of game play. As the ability of the subject to use the amblyopic eye improves, game performance is expected to increase, and therefore the contrast setting in the fellow-eye will increase. The lower limit of fellow-eye contrast is set at 10%, which corresponds to the lower limit of the visible threshold for viewing objects on the screen. If the fellow-eye contrast remains at 10% for a period of 7 days, the game will show an alert for parents to contact their eye care provider.

3.1.1 Binocular Treatment Group

Subjects assigned to the binocular treatment group will be prescribed the Hess Falling Blocks game to play for 1 hour per day, 7 days a week (with a minimum of 4 days a week for children unable to play 7 days a week) for 16 weeks. Parents of subjects will be instructed that the 1 hour of daily treatment should be completed in a single 60-minute session, but if this is not possible for whatever reason, the treatment may be divided into shorter sessions totaling 1 hour. The difficulty setting (easy, medium, or hard) is at the discretion of the child.

3.1.2 Patching Group

Subjects assigned to the patching group will wear an adhesive patch over the fellow eye for 2 hours per day, 7 days per week for 16 weeks. Parents of subjects will be instructed that the 2 hours of daily patching should be completed in a single 2-hour session, but if this is not possible for whatever reason, the treatment may be divided into shorter sessions totaling 2 hours.

3.2 Compliance

Parents will be asked to complete a compliance calendar by manually recording the number of minutes that the child played the game each day or how long the patch was worn. The investigator will review the calendars at each follow-up visit. The amount of time the game is played will also be recorded automatically during game play by the iPad. These data will be downloaded at the site during each follow-up visit when the iPad is brought to the study visit.

3.3 Phone Call

Site personnel will call all subjects at 1 week (7 to 13 days) to encourage compliance with treatment and to confirm that there are no technical problems playing the binocular game for those assigned to binocular treatment.

3.4 Follow-up Visit Schedule

The follow-up schedule is timed from randomization as follows:

- 4 weeks \pm 1 week
- 8 weeks \pm 1 week
- 12 weeks \pm 1 week
- 16 weeks \pm 1 week

Subjects achieving amblyopic-eye visual acuity equal to or better than the fellow-eye visual acuity (0 lines or more lines better, 0 letters or more better if E-ETDRS) and at least 20/25 (or \geq 78 letters if E-ETDRS) visual acuity in both eyes will be considered to have resolved and will discontinue treatment, although these subjects will still return for all remaining follow-up exams. If at a subsequent visit there is regression of amblyopia (2 logMAR lines or 10 letters from best previous visual acuity), treatment will be restarted.

Additional non-study visits can be performed at the discretion of the investigator.

3.5 Follow-up Visit Testing Procedures

Subjects will be seen at follow-up visits as outlined in *section 3.4*. A Masked Examiner must complete distance visual acuity and stereoacuity testing at these visits (*section 3.5.1*). All procedures will be performed with the subject's current refractive correction. If a subject currently wears spectacles but is not wearing them at the follow-up examination for whatever reason, testing must be performed in trial frames.

Prior to the Masked Examiner entering the room, subjects and parents should be instructed not to discuss their treatment with the Masked Examiner.

The following procedures should be performed at each visit:

1. Diplopia Questionnaire

- The child and parent(s) will be specifically questioned regarding the presence and frequency of any diplopia since the last study visit using a standardized diplopia assessment (*see ATS Miscellaneous Testing Procedures Manual*). The diplopia assessment must be performed prior to any other testing during the exam.

2. Distance Visual Acuity Testing (masked):

- Monocular distance visual acuity testing will be performed in habitual refractive correction in each eye using the same visual acuity testing method that was used at enrollment, as described in the *ATS Testing Procedures Manual*.
 - Testing must be completed without cycloplegia.

3. Stereoacuity Testing (masked):

- Stereoacuity will be tested in habitual current refractive correction using the Randot Butterfly test and Randot Preschool Stereoacuity test at near (1/3 meter).

4. Ocular Alignment Testing:

- Ocular alignment will be assessed in habitual refractive correction by the cover/uncover test, simultaneous prism and cover test (SPCT), and prism and alternate cover test

(PACT) in primary gaze at distance (3 meters) and at near (1/3 meter) as outlined in the *ATS Procedures Manual*.

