3.5.1 Masked Examiner

The Masked Examiner must be certified to test visual acuity and stereoacuity. Because the Masked Examiner must be masked to the subject's treatment group, he/she must be someone other than the managing clinician (in many cases the managing clinician will be the investigator but this is not required).

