5.4.7.2 Ocular Alignment

The proportion of subjects with development of new strabismus (no heterotropia at baseline and the presence of near and/or distance heterotropia at 16 weeks) or an increase from baseline $\geq 10\Delta$ in a pre-existing strabismus will be reported by treatment group and compared using the Fisher exact test.

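### Masking is required for acuity and stereoacuity but not for ocular alignment, so an examiner who knows the arm may make the call that defines new strabismus

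*Protocol*

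**What the plan says.** Protocol section 3.5 sets out four procedures for each follow-up visit. Its opening paragraph requires that "A Masked Examiner must complete distance visual acuity and stereoacuity testing at these visits", and the headings for those two tests carry the label (masked). The fourth item carries no such label: "Ocular alignment will be assessed in habitual refractive correction by the cover/uncover test, simultaneous prism and cover test (SPCT), and prism and alternate cover test".

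Section 3.5.1 follows the same division. It says "The Masked Examiner must be certified to test visual acuity and stereoacuity" and does not name alignment. It adds: "Because the Masked Examiner must be masked to the subject's treatment group, he/she must be someone other than the managing clinician". That keeps the managing clinician out of the Masked Examiner role. It does not keep the managing clinician from doing the cover tests.

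Section 5.4.7.2 then uses alignment as a safety outcome: "The proportion of subjects with development of new strabismus (no heterotropia at baseline and the presence of near and/or distance heterotropia at 16 weeks". A second component counts strabismus already present that has grown by at least 10 prism dioptres. The proportions are compared between arms with the Fisher exact test. Section 2.5 explains why randomization is not stratified by tropia: "diagnosis of a microtropia is problematic".

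**The concern.** New strabismus is a yes/no judgement with no minimum angle. Section 2.2.1 limits enrolment to children with a total near deviation of 10 prism dioptres or less, so small deviations near the limit of detection are to be expected. The baseline examination comes before randomization, when no examiner can know the arm. The 16-week examination comes after it and may be done by someone who does. If knowing the arm moves the threshold for calling a small tropia, it does so after baseline and possibly in one arm only.

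What is at stake is one between-arm safety comparison. A difference in detection could produce an apparent harm of either treatment or hide a real one. An analysis plan cannot restore masking afterwards. At best it can separate masked from unmasked assessments, and only if masking status was recorded.

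**Working it through.** **Step 1: which safety outcomes are exposed.** Section 5.4.7 lists three.

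| Outcome | Who determines it | Masking required? |
|---|---|---|
| Fellow-eye acuity (5.4.7.1) | Examiner; each eye tested | Yes, under the acuity item of 3.5 |
| Ocular alignment (5.4.7.2) | Examiner, by cover tests | No |
| Diplopia (5.4.7.3) | Child and parent, by standardized questions | No, but the respondents know the arm anyway |

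Alignment is thus the only examiner-judged safety outcome without a masking requirement. Within it, the two components differ. New heterotropia is a yes/no call of any size. An increase of at least 10 prism dioptres is a measured change against a stated threshold and is less exposed.

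**Step 2: illustration of size.** The protocol gives no rate of new strabismus and no power for this outcome, so there is no stated figure to reproduce. Inputs:

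- Evaluable children per arm: 155 in the younger cohort (section 5.2.1) and 70 in the older cohort (section 5.2.2). Section 5.1 says the cohorts are analysed separately.
- Assumed true rate of new strabismus: p = 5% in both arms.
- Assumed called rate in one arm: q = 5% (no bias), 7.5% or 10%. The other arm stays at 5%.

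If a share x of unaffected children in one arm is over-called, q = p + (1 − p)x, so x = (q − p)/(1 − p). For q = 7.5%, x = 0.025/0.95 = 2.6%. For q = 10%, x = 0.05/0.95 = 5.3%.

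The probability of a falsely significant result is the exact sum, over all pairs of counts (i, j) whose two-sided Fisher p-value is at most 0.05, of Bin(i; n, 0.05) × Bin(j; n, q).

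| n per arm | q = 5% | q = 7.5% | q = 10% |
|---|---|---|---|
| 155 | 2.5% | 9.8% | 31.1% |
| 70 | 1.4% | 3.9% | 11.4% |

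In children, at 155 per arm the expected excess is 155 × 0.025 = 3.9 for q = 7.5% and 155 × 0.05 = 7.8 for q = 10%. At 70 per arm it is 1.8 and 3.5.

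**Step 3: sensitivity to the assumptions.** Only children without heterotropia at baseline can develop it. If that is half of the younger cohort (about 78 per arm, an assumption), the three figures become 1.6%, 4.6% and 13.7%. With a true rate of 2%, called at 4% in one arm, the result is 9% at 155 per arm and 1.8% at 70. The mildest scenarios in the smaller samples therefore stay below the nominal 5%.

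**The case against.** The strongest reply is that this is a visible design choice on a secondary safety table. The primary outcome, fellow-eye acuity and stereoacuity are all masked. No success criterion or stopping rule in the protocol is tied to alignment, and section 4.7.1 classes the study as minimal risk. All of that stands, and it limits the weight of the point.

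Four stronger readings are tempting but not supported:

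- *Alignment is in fact assessed unmasked.* A reader might infer this from the missing label. The text only fails to require masking. It does not say who performs the cover tests, a site could use the Masked Examiner, and the procedures manual cited for technique is not at hand.
- *Masking status goes unrecorded.* The Follow-up Examination Form is mentioned in section 4.5 but not shown, so its contents cannot be asserted.
- *The protocol itself points to bias in one arm.* Section 4.6 speaks of a manifest deviation only conditionally, and the visible text names no arm. The remark in section 2.5 concerns diagnostic difficulty in general, which is equally compatible with error that is the same in both arms.
- *The safety comparison is severely distorted.* Tripling the called rate in one arm, from 5% to 15%, would give false significance in 81% of trials at 155 per arm. Nothing in the protocol supports over-calling of that size.

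It is also fair to say that the remedy is partial: sites without a suitably qualified Masked Examiner would still have unmasked calls. What survives is that the protocol permits an avoidable source of bias in a formal between-arm comparison.

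**Conclusion.** The point holds as a minor one. Following the protocol as written, an examiner who knows the arm may decide whether a child has new strabismus. The judgement has no minimum angle, and the protocol itself describes the diagnosis of small tropias as difficult.

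Neither the direction nor the size of any bias can be known from the protocol. The figures show only that a few extra calls in one arm could matter: false significance in about 10% to 31% of trials at 155 per arm and 4% to 11% at 70 per arm. They rest wholly on the assumed 5% true rate, on over-calling confined to one arm, and on all evaluable children being at risk. They should not be read as an estimate of what will happen. The conclusion does not extend to the primary outcome, and it applies less to the component defined by a 10-prism-dioptre increase.

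**What to change.** 1. In section 3.5, have the existing Masked Examiner do the follow-up cover/uncover test, at least at 16 weeks, wherever that person is qualified in cover testing.
2. Elsewhere keep the current examiner, and record masked yes/no on the Follow-up Examination Form if it does not already do so.
3. In section 5.4.7.2, add a sensitivity comparison restricted to masked assessments, and state the unmasked assessments as a limitation.

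The cost is a short protocol change, possibly one form field, and one extra table. A Masked Examiner is already required at every follow-up visit, so no staff are added. The downside is that some Masked Examiners will not be qualified in cover testing, since section 3.5.1 certifies them only for acuity and stereoacuity. The masked-only comparison will therefore be smaller and have less power. Clinical handling of any new deviation stays as the protocol has it.

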3.5.1 Masked Examiner

The Masked Examiner must be certified to test visual acuity and stereoacuity. Because the Masked Examiner must be masked to the subject's treatment group, he/she must be someone other than the managing clinician (in many cases the managing clinician will be the investigator but this is not required).

3.6 Non-Study Visits and Treatment

Investigators may schedule additional visits at their own discretion. Subjects will continue to follow the study-specified follow-up schedule regardless of any non-study visits. No data will be collected at non-study visits for the purpose of the study.

Investigators must not start any additional treatment (other than that outlined in *section 3.1*) prior to the 16-week outcome visit.

CHAPTER 4: MISCELLANEOUS CONSIDERATION IN FOLLOW-UP

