4.2 Game Alerts

In the event that the subject is unable to successfully play the game for whatever reason (e.g., failure of amblyopia to improve, worsening of amblyopic eye, inattention of subject), contrast of the fellow eye will automatically decrease in 10% increments, to as low as 10%, which corresponds to the lower limit of the visible threshold for viewing objects on the screen. If the game settings remain at 10% for a period of 7 days, the game will show an alert for parents to contact their eye care provider. Investigators should assess the cause for the inability to play the game. As appropriate, investigators may choose to examine the subject at their discretion and contact the Jaeb center for technical assistance if deemed necessary. Investigators will offer encouragement to the child and parents to continue treatment as best they are able.

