If treatment precipitates the development of a manifest ocular deviation (e.g., esotropia) and/or diplopia, the parent will be advised to have the subject see the investigator as soon as possible. If a new manifest deviation is confirmed on examination, the decision as to whether to continue or discontinue therapy will be left to the investigator's and parent's decision. If the investigator determines that binocular diplopia is present, continuation of treatment is also at the discretion of the investigator and parent(s). If amblyopia treatment is to be discontinued during the study, a Protocol Chair should be called to discuss the case. Subjects discontinuing treatment during the study will continue to be seen for the remaining regularly scheduled study visits.

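### A new deviation confirmed between scheduled visits, and the date and reason for stopping treatment because of harm, have no stated place in the trial data

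*Protocol*

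**What the plan says.** Protocol 3.4 fixes study visits at 4, 8, 12 and 16 weeks, each with a window of one week either side, and adds: "Additional non-study visits can be performed at the discretion of the investigator". Protocol 3.6 then sets the data rule for such visits: "No data will be collected at non-study visits for the purpose of the study".

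The risk text of chapter 4, in the paragraph just before 4.6.2, deals with a manifest deviation or diplopia brought on by treatment. In that case "the parent will be advised to have the subject see the investigator as soon as possible". What follows is conditional on that examination ("If a new manifest deviation is confirmed on examination"), and the investigator and parent then decide whether treatment continues. On stopping, it says: "If amblyopia treatment is to be discontinued during the study, a Protocol Chair should be called to discuss the case". It also says: "Subjects discontinuing treatment during the study will continue to be seen for the remaining regularly scheduled study visits".

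At each scheduled visit (3.5), child and parents are "specifically questioned regarding the presence and frequency of any diplopia since the last study visit using a standardized diplopia assessment", and alignment is tested by cover/uncover, SPCT and PACT. New strabismus and diplopia are safety outcomes in 5.4.7.2 and 5.4.7.3.

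**The concern.** The protocol's own route for a suspected deviation or diplopia leads to an examination that will often fall between scheduled visits. The rule in 3.6 is an express bar on data from such visits, not a silence that a later analysis plan could fill, because no plan can analyse what the protocol says is not collected.

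At stake is the completeness of the safety description for harms that the protocol itself foresees. The children affected would be those who were seen promptly, as the protocol asks, and whose deviation then settled. It also matters for reading the results of children who stopped treatment: without a date and a reason, a stop for harm cannot be told from loss of interest. In the younger cohort, 5.2.1 cites the absence of safety concerns as one reason for having no interim monitoring, which is a further reason to keep these data complete.

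**Working it through.** No stated figure is in dispute, so there is none to reproduce. The check sets the provisions side by side and does some arithmetic on the visit schedule.

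**1. Is the prompt examination a non-study visit?** The study visits are the four in 3.4, and 3.4 calls additional visits non-study. An examination for a suspected deviation or diplopia that does not coincide with one of the four is additional. The risk text does not itself use the label, so this is an inference, but 3.4 and 3.6 leave no third kind of follow-up visit.

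**2. What do the other provisions recover?**

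| Event between visits | Later provision | Recovered? |
|---|---|---|
| Diplopia | Questionnaire looks back to the last study visit (3.5) | Yes, as reported presence and frequency |
| Deviation still present at the next scheduled visit | Alignment testing (3.5); follow-up continues after a stop | Yes |
| Deviation settled by the next scheduled visit | Alignment testing is point-in-time, with no look-back | No |
| That treatment ceased | iPad log (game arm) and parent calendar (3.2) | Approximately |
| Formal date of the stop, and its reason | Call to a Protocol Chair; no record named | No stated route |

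Section 4.7 refers adverse events to local IRB requirements and names no study record. Section 4.5 shows the contrast: strabismus surgery, also an off-schedule event, is to be written in the comment section of the Follow-up Examination Form.

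**3. How long can a deviation go unseen?** The windows are weeks 3–5, 7–9, 11–13 and 15–17.
- Nominal gap between consecutive visits: 8 − 4 = 4 weeks.
- Longest: 9 − 3 = 6 weeks.
- Shortest: 7 − 5 = 2 weeks.

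**4. Illustration of the mechanism (durations assumed; the protocol gives none).** If onset is uniform within a gap of g weeks and the deviation lasts d weeks, the chance that it is present at the visit closing the gap is the smaller of d/g and 1.

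| d (weeks) | g = 4 | g = 6 | g = 2 |
|---|---|---|---|
| 1 | 1/4 = 25% | 1/6 = 17% | 1/2 = 50% |
| 2 | 2/4 = 50% | 2/6 = 33% | 100% |
| 3 | 3/4 = 75% | 3/6 = 50% | 100% |

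At the nominal spacing, a deviation lasting 4 weeks or more is always seen, provided it begins early enough to reach a remaining visit. These are chances given a duration. They do not give a number of lost events, which would also need event rates and the distribution of durations.

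**5. Which planned analysis is affected?** Section 5.4.7.2 defines new strabismus by heterotropia at 16 weeks. A deviation that settles before then is not counted there, whether or not the interim examination was recorded. The loss therefore falls on the trial's record of harms, and not on the strabismus comparison as currently defined.

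**The case against.** The strongest case on the other side is that the scheduled visits do most of the work. A reader might infer from 3.6 that harms seen between visits never reach the safety data. The protocol does not support that: diplopia is asked about over the whole interval, persisting deviations are re-examined, and children who stop treatment stay in follow-up. All of this stands, and it confines the point to transient deviations and to the date and reason for a stop.

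Second, the 16-week definition in 5.4.7.2 means that no planned strabismus count changes. That is correct. It is why the remedy should add a descriptive report and not alter that comparison.

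Third, a recording route may exist elsewhere. The opening of the risk section was not in the text examined here, nor were the case report forms and procedures manuals. This limits any claim that no route exists. It does not remove the need to qualify 3.6, whose wording is unconditional.

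Fourth, a reader might extend the point to game alerts, where under 4.2 "investigators may choose to examine the subject at their discretion". That does not follow. Alerts concern inability to play, with causes such as inattention or lack of improvement, and the examination is optional. They are not primarily a route for detecting harm.

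Finally, a reader might want the share of events lost. Any such figure would rest on assumed event rates and durations, and the document supplies neither.

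**Conclusion.** The point holds in a limited form. Section 3.6 bars data at non-study visits with no safety exception, while the risk text directs a suspected new deviation or diplopia to an examination that will usually be such a visit. The two need to be reconciled. What is lost is (a) any deviation confirmed between visits, nominally 4 and at most 6 weeks apart, that settles before the next scheduled examination, and (b) a stated record of the date and reason for a harm-related stop. Diplopia reports and persisting deviations are not lost. The number of events affected cannot be estimated from the protocol.

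The conclusion rests on two assumptions: that the prompt examination counts as a non-study visit when it falls off schedule, and that no form or manual outside the visible text already overrides 3.6.

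**What to change.** Add an exception to 3.6: any visit prompted by a suspected new deviation or diplopia is recorded, giving its date, the alignment findings if testing was done, and whether, when and why assigned treatment was stopped. The record can be a short form or an entry on the next Follow-up Examination Form, as 4.5 already does for surgery. Add a cross-reference in the risk text so that the two sections agree. If an existing form already captures this, citing it in 3.6 is enough.

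Report these events descriptively by arm, separately from the scheduled-visit results in 5.4.7.2 and 5.4.7.3, and do not pool them into the Fisher exact tests. The examinations are unmasked, and families know the assigned treatment, so the tendency to come in may differ by arm. Pooling could also count diplopia twice, since the questionnaire already covers the interval.

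The cost is one sentence, one cross-reference and a few fields, applied only to examinations that take place anyway. No visit, treatment decision or planned comparison changes.
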